4.4. Safety Reporting

441 **Adverse Events**

All adverse events will be collected during this registry. Safety definitions used during this Registry will be per the definitions in ISO 14155 and are provided in Table 1 and Table 2.

Table 1: Safety Reporting Definitions

Adverse Event	Any untoward medical occurrence, unintended disease or injury, or untoward clinical signs (including abnormal laboratory findings in subjects, users or other persons, whether or not related to the study device			
	NOTE For users or other persons, this definition is restricted to events related to the study device.			
Adverse Device Effect	Adverse event related to the use of the study device			
	NOTE 1 This definition includes adverse events resulting from insufficient or inadequate instructions for use,			

	deployment, implantation, installation, or operation, or any malfunction of the study device. NOTE 2 This definition includes any event resulting from use
	error or from intentional misuse of the study device.
Serious Adverse Event	Adverse event that a) led to death, b) led to serious deterioration in the health of the subject, that either resulted in 1) a life-threatening illness or injury, or 2) a permanent impairment of a body structure or a body function, or 3) in-patient or prolonged hospitalization, or 4) medical or surgical intervention to prevent life-threatening illness or injury or permanent impairment to a body structure or a body function, c) led to fetal distress, fetal death or a congenital abnormality or birth defect.
	NOTE This includes device deficiencies that might have led to a serious adverse event if a) suitable action had not been taken or b) intervention had not been made or c) if circumstances had been less fortunate. These are handled under the SAE reporting system.
Serious Adverse Device Effect	Adverse device effect that has resulted in any of the consequences characteristic of a serious adverse event
Unanticipated Serious Adverse Device Effect	Any serious adverse effect on health or safety or any life- threatening problem or death caused by, or associated with, a device, if that effect, problem, or death was not previously identified in nature, severity, or degree of incidence in the investigational plan or application (including a supplementary plan or application), or any other unanticipated serious problem associated with a device that relates to the rights, safety, or welfare of subjects.
Device deficiency	Inadequacy of a medical device with respect to its identity, quality, durability, reliability, safety or performance. NOTE Device deficiencies include malfunctions, use errors, and inadequate labelling.

For all AEs the Investigator must determine whether the event was related to the device and/or procedure. Individual events may be related to more than one category, e.g. an injury due to a tunneling tool may be related to Device Hardware and Procedure. The categories used for relatedness are listed in Table 2.

Table 2: Adverse Event Relatedness Categories

Related to Device					
Related to Device Hardware	Events reasonably anticipated to be related to the physical presence of the device, e.g. erosion, or a device malfunction, e.g. loss of power.				
Related to Device Stimulation	Events reasonably anticipated to be related to electrical stimulation, especially those that appear when the device				

	is on and disappear when the device is off, e.g. undesired sensation experienced only when the device is turned on.			
Related to Procedure				
Related to Procedure	Events reasonably anticipated to be related to procedures described in the labeling.			

4.4.2. Unavoidable Events

Adverse Events that would be reasonably expected to be associated with any surgical procedure will not be categorized as procedure or device related in the 30 days after a surgical procedure (e.g.: device implant, explant, or revision). These may include the following:

- Anesthesia related nausea/vomiting within 24 hours
- Low-grade fever within 48 hours
- Incisional pain within 72 hours
- Mild to moderate bruising/ecchymosis of surgical sites within 72 hours
- Sleep problems within 72 hours
- Muscle pain related to lying on table within 72 hours
- Mild swelling and/or drainage from incision within 48 hours
- Numbness medial to incisions that occur immediately post-procedure
- Pain/irritation/minor bleeding during removal of sutures
- Urinary retention immediately post-procedure with removal of the Foley catheter
- Constipation and/or dehydration that may occur within 72 hours

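### Section 4.4.2 bars relatedness for 30 days with an open list and no seriousness limit, so read literally a serious early surgical event could leave the SADE count

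*Protocol*

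**What the plan says.** Section 4.4.1 of the Protocol sets the general duty: "For all AEs the Investigator must determine whether the event was related to the device and/or procedure". Table 2 then offers device hardware, device stimulation and procedure as categories, and one event may carry more than one of them.

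Section 4.4.2 follows directly. Adverse events that one would reasonably expect after any operation "will not be categorized as procedure or device related in the 30 days after a surgical procedure"; implantation, removal and revision are given as examples of such procedures. Eleven examples are introduced by "These may include the following". Neither section refers to the other, and 4.4.2 does not mention seriousness.

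Table 1 defines a SADE as: "Adverse device effect that has resulted in any of the consequences characteristic of a serious adverse event". An ADE is in turn an adverse event related to use of the device.

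The Registry Summary and Section 4.1 make reporting of all SADEs the safety purpose. Section 4.4.4 builds the annual Notified Body report and the stated vigilance step on SADEs.

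**The concern.** Relatedness is the gate to the registry's only stated safety measure. If a coding rule sets relatedness to no for a class of events, none of them can become an ADE or a SADE, however serious. The class in 4.4.2 is bounded only by a judgement of what is to be expected after surgery and by a 30-day window. The early period after surgery is also when serious events linked to implantation are plausible.

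Two things are at stake. A serious early event might be missing from the SADE count and from the reports drawn from it. In addition, with up to 25 sites and an open list, the same event might be coded differently from site to site.

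**Working it through.** **1. The plan's own figure.** Section 4.8 states 80% power to see at least one event with 50 Subjects at a rate of 3.2%. Check: 1 − (1 − 0.032)^50 = 1 − 0.968^50 = 0.803. The figure reproduces and is not in dispute. It concerns events of any kind, so it does not measure the effect of 4.4.2.

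**2. The window against the examples.** The limits stated in the 4.4.2 list are:

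| Limit | Examples | Count |
|---|---|---|
| 24 h | nausea/vomiting | 1 |
| 48 h | fever; swelling/drainage | 2 |
| 72 h | incisional pain; bruising; sleep problems; muscle pain; constipation/dehydration | 5 |
| Circumstance only | numbness; suture removal; urinary retention | 3 |

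The total is 1 + 2 + 5 + 3 = 11. Ten of the 11 fall within 72 h or immediately after the procedure; only suture removal can come later. The longest hour limit is 72 h = 3 days, and 30 / 3 = 10. The examples therefore do not explain a 30-day window.

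**3. Severity.** Four of the 11 examples carry a severity word (fever, bruising, swelling, bleeding). The other 11 − 4 = 7 carry none. Two of those seven are "Constipation and/or dehydration that may occur within 72 hours" and "Urinary retention immediately post-procedure with removal of the Foley catheter".

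**4. Can an exempt event be serious?** Table 1 counts an event as serious if it causes a serious deterioration in health that results in, among other outcomes, "in-patient or prolonged hospitalization". Most listed items will never meet this. Dehydration or urinary retention could, in an unusual case. As written, 4.4.2 would still withhold relatedness, and because the list is open the same holds for unlisted events judged to be expected.

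**5. The chain of definitions.** 4.4.2 applies → neither procedure nor device relatedness is assigned → not an ADE → not a SADE → absent from the safety measure and from the SADE-based reports in 4.4.4. The chain matters only if the event would have been an ADE without 4.4.2. For an event due solely to the procedure, this turns on NOTE 1 to the ADE definition, which speaks of inadequate instructions for use and then of "deployment, implantation, installation, or operation, or any malfunction of the study device". If the inadequacy wording governs implantation too, a complication of a properly done implantation is not an ADE and no SADE is lost. If it does not, the event is an ADE.

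**6. Size.** The documents give no rate or share of serious events that 4.4.2 would catch, so the number lost cannot be derived and may be zero. Assuming one event per Subject, each relabelled event moves the SADE rate by 1/50 = 2.0 percentage points. This is a maximum, because 50 is the minimum enrolment; with an assumed 100 Subjects it is 1/100 = 1.0 point. This is simply the weight of one event, not an estimate of loss.

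**The case against.** A reader might infer that 4.4.1 and 4.4.2 flatly contradict each other. They need not: a general duty followed at once by a specific rule is ordinary drafting, and 4.4.2 can be read as the exception. That objection stands. What remains is that neither section says so and that the exception has no firm edge.

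A reader might also infer that SADEs will be lost. The documents do not show this. The heading, the expectedness test and the mild character of the examples all point to trivial events. Events specific to the device or to stimulation fall outside the rule. The SADE step for procedure-only events depends on NOTE 1. Sections 4.4.1 and 4.4.3 still require every AE to be collected and reported to the Sponsor, so a miscoded event can be found and reclassified. These points stand and limit the weight of the concern.

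A third tempting inference is that an infection at the activation visit, around day 14, is exempt. Section 4.7.2 mentions infection only as a reason to postpone activation. It does not call it surgical, expected or covered by 4.4.2, so it is no evidence of an exempted event.

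None of these points supplies the missing seriousness limit or explains the 30 days. The intent to cover only minor events is plausible, but it is not written down.

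**Conclusion.** The point holds as a defect in a coding rule, not as a demonstrated bias. Section 4.4.2 has an open list, no seriousness limit, and a window 10 times the longest hour limit of its own examples. Literal use could remove a serious early surgical event from the SADE count and the SADE-based reports.

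This rests on three conditions: the event is judged to be expected after any surgery, it meets the SAE definition, and it would otherwise be an ADE. The documents do not say how often all three would be met. The event would remain in the AE data. The defect should be fixed because the affected quantity is the registry's stated safety measure and the repair is nearly free.

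**What to change.** Reconcile 4.4.1 and 4.4.2 as follows.

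- In 4.4.2, delete the general 30-day window and replace the illustrative lead-in with a closed list, for example: *Only the non-serious events listed below, when they occur within the time or circumstance stated for each, are exempt from categorisation as procedure or device related.*
- Add to 4.4.2: *Any event that meets the SAE definition, or that falls outside its listed limit, has its relatedness determined under Section 4.4.1.*
- In 4.4.1, after the sentence on determining relatedness, add: *Section 4.4.2 is the only exception.*

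No new CRF field is needed, and Table 1, which follows ISO 14155, can stay as it is. The edit restores the relatedness decision for serious events whichever way NOTE 1 is read. The cost is a one-paragraph amendment and a cross-reference. The count of related events may be slightly higher, because later or unlisted events will no longer be exempt.

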4.4.3. Reporting by the Investigator

The Investigator shall report to the Sponsor all AEs The sites are obliged to forward as soon as possible, in a follow-up report, any AE-related information (e.g. outcome) that may have been missing at the time of the initial report as the event is recorded at the site.

4.4.4. Reporting by the Sponsor

All SADEs reported in the Registry will be reported to the Notified Body on an annual basis.

SADEs that meet the criteria of an Incident per MEDDEV 2.12/1 (Revision 8) shall be reported as part of Vigilance reporting to the relevant competent authority and to the Notified Body. Vigilance reportable events will be reviewed for reporting requirements in other applicable geographies outside of the European Union.

4.5. Performance Measures

Documentation of performance of ReActiv8 is by reporting on the measures summarized below.

4.5.1. Low Back Pain – NRS

Average Low Back Pain will be measured using the 11-point Numerical Rating Scale for Low Back Pain (Figure 1), as recommended by IMMPACT.⁴⁰ Specifically, the NRS scale for "average low back pain in the last 24 hours" will be used.

							_	_		
0		_	_		_	_	_	_	_	
n	1	2	3	4	5	I 6	7	- 2	a	10
U		_	0	-	-		- 1	0	9	10

Please rate your average low back pain in the last 24 hours on a scale from zero to ten, where zero is no pain and ten is your worst imaginable pain.

Figure 1: 11 Point Numerical Rating Scale for Low Back Pain

4.5.2. Disability – ODI

Disability is measured using the Oswestry Disability Index (ODI). ODI is a disease specific assessment of the disabling effects of back pain utilizing a questionnaire consisting of 10 sections: pain intensity, personal care, lifting, walking, sitting, standing, sleeping, sex life (if applicable), social life, and travelling. Each section consists of six statements correlating to scores of 0 through 5, with the Subject choosing the statement that matches his or her ability. The statement correlating with a score of 0 indicates the least disability, and the statement correlating to 5 represents the greatest disability. Scores from 0% to 20% indicate minimal disability; 21% to 40%, moderate disability; 41% to 60%, severe disability; 61% to 80%, crippled; and 81% to 100%, bedbound or exaggerating.

4.5.3. Quality of Life – EQ-5D

EQ-5D is the acronym for the European Quality of Life Score on Five Dimensions. Descriptive system of health-related quality of life states consisting of five dimensions (mobility, self-care, usual activities, pain/discomfort, anxiety/depression) each of which can take one of five responses. The responses record five levels of severity (no problems/slight problems/moderate problems/severe problems/extreme problems) within a particular EQ-5D dimension. The EQ-5D Index is scored on a scale from -0.59 to 1.00, with a score of 1.00 indicating full health.

4.5.4. Percent Pain Relief (PPR)

Percent Pain Relief (PPR) is a question regarding that Subject's perception of how much better the Subject's back pain is compared to the time of baseline in the Registry, where 0% is no improvement, and 100% is no low back pain.

4.5.5. Subject Global Impression of Change (SGIC)

The SGIC is a question regarding the Subject's impression of how their condition has changed since baseline on a scale of 1 (much better) to 7 (much worse). Therefore, a decreased score on this measurement indicates an improvement.

4.5.6. Treatment Satisfaction Questionnaire (TSQ)

The TSQ is a questionnaire used to find out if a Subject is satisfied with the treatment based on a yes/no question. Therefore, a higher percent indicates that more Subjects in the Study are satisfied with the treatment. In addition, Subjects who indicate that they are satisfied with the treatment are asked if they are "satisfied" or "very satisfied".

4.6. Health Care Utilization

Cost-effectiveness data will be collected for ReActiv8 at baseline and the annual visits post-activation, to be extrapolated to the lifetime of the device. The key economic outcome measures to be recorded will be:

- 1. Work status
- 2. Use of Opioids
- 3. Health Care Utilization (office visits, hospital visits and other therapies such as physical therapy)

4.7. Data Collection Schedule

The data for the registry will be collected according to the following schedule:

Visit 1: Baseline visit

Visit 2: Activation visit (approximately 14 days post-surgery)

Visit 3: 90±30 days Post-Activation

Visit 4: 180±30 days Post-Activation

Visit 5: 1 year±60 days Post-Activation

Visit 6: 2 years ±60 days Post Activation

The above mentioned visits are part of the standard of care for patients with this type of treatment. The given time windows are advisable and data collection outside these windows will not be seen as a protocol deviation.

Any unscheduled visits will be recorded as stated in Table 3 and in section 4.7.6.

Note that data collection of all performance measures shall be done as the first thing in the follow up visit, prior to any other procedures.

Note that once a Subject has consented to participate in the Registry Adverse Events will be collected at each visit.

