Safety, Performance, Health Utilization Measures	 Assessment of all Serious Adverse Device Effects that occur through two years post-implant. Performance Change in average low back pain from baseline to follow-up visits (NRS) Change in Oswestry Disability Index from baseline to follow-up visits (ODI) Change in EQ-5D from baseline to follow-up visits (EQ-5D) Assessment of Percent Pain Relief at follow-up visits (PPR) Assessment of Subject Global Impression of Change at follow-up visits (SGIC) Assessment of Patient Treatment Satisfaction at follow-up visits (TSQ) Health Care Utilization Change in work status from baseline to follow-up visits Change in use of opioids from baseline to follow-up visits Assessment of Health Care Utilization (office visits, hospital visits, imaging and diagnostics and other pain management treatments) at follow-up visits 						
Study Visit Schedule	 Visit 1: Baseline visit Visit 2: Activation visit: Approximately 14 days post-surgery Visit 3: 3 month visit: 90±30 days post-activation Visit 4: 6 month visit: 180±30 days post-activation Visit 5: 1 year visit: 1 year±60 days post-activation Visit 6: 2 year visit: 2 year±60 days post-activation 						

2. Background

Mainstay Medical has developed an implantable medical device designed as therapy for people with chronic low back pain (CLBP). The device, called ReActiv8®, consists of two implantable leads with four electrodes each, configured to deliver electrical stimulation to the medial branch of the dorsal ramus nerves as they cross the transverse process at L3 to elicit bilateral contraction of the lumbar multifidus muscles (MF). The leads are coupled to a battery powered implantable pulse generator (IPG) which is activated by an external Activator and is programmed using Application Software provided on a laptop computer. Several accessories are included as part of the system, for example to facilitate the surgical procedure.

The therapy delivered by the ReActiv8 was explored with a European Feasibility Study in 2011 to 2013 using "off the shelf" general purpose neurostimulation devices from other manufacturers, and results have been published.¹

ReActiv8 was investigated under an ongoing clinical trial at nine sites in Australia and Europe (ReActiv8-A). The data from the first 47 Subjects implanted with ReActiv8 in this trial served as the basis for CE Marking on 24-May-2016. A summary of the ReActiv8-A Trial can be found at http://clinicaltrials.gov/show/NCT01985230.

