4.1. Objective

To gather data on the long-term safety of ReActiv8 and identify any residual risks by reporting all Serious Adverse Device Effects as well as performance and health care utilization through two years post-implant.

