4.2. Overview

The ReActiv8 Registry is an international, multi-center, data collection registry in Subjects who meet the CE Mark indications and are not contraindicated for ReActiv8. A minimum of 50 Subjects will be implanted at up to 25 sites. Subjects will be followed for two years postimplant, at which time they will be exited from the Registry. Subjects may decide to be enrolled in the registry before or after implant so that information on the performance of the system can be collected.

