4.7.1. Visit 1: Baseline Visit

The process for obtaining informed consent shall be in compliance with ISO 14155.

If the subject agrees to participate in the registry for data collection, the Subject Informed Consent will be signed and recorded in the Subject's records at Visit 1. The Subject will be assigned a unique Registry identifier and will be asked to complete the baseline questionnaires.

Data will be collected according to the data collection schedule (Table 3).

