4.7.2. Visit 2: Activation Visit (≈ 14 days Post Implant)

Activation of the therapy shall be about 14 days from the date of implant surgery.

If the Subject is unable to use the device for any reason (e.g.: injury, infection, other new clinical condition) at the time of the activation visit, then the activation visit may be postponed to allow the issue to resolve. This will not be considered a deviation.

Activities to be performed:

- Perform electrode impedance and threshold measurements and record results
- Program IPG
- Train the Subject in use of the Activator, and document assessment of Subject's ability to self-administer therapy. Instruct Subject on timetable of therapy delivery (i.e.: twice a day starting the next day).
- Train the Subject in the procedure to deliver stimulation, including time of day and Subject positioning.

Data will be collected according to the data collection schedule (Table 3).

Visits 3 and 4: 90 ± 30 Days and 180 ± 30 Days Post 4.7.3. Activation

During this visit data will be collected according to the data collection schedule (Table 3) and the following activities will be performed:

Device activities (if applicable):

- Electrode impedance and threshold measurements
- Readout from IPG of therapy delivery times and duration
- Adjustment of stimulation configuration and amplitude as appropriate

If a subject is unable to return to the clinic for an annual office visit, the clinical site may send the questionnaires to the subject for completion and a telehealth visit may be completed by the investigator and study coordinator.

Device interrogation and programming will be done at a later date when the subject is able to return for a visit.

If programming is completed it will be entered on the annual visit form. It will not be a deviation when the interrogation and programming of the system is required at a later date.

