4.7.6. Unscheduled Visits

If an unscheduled visit occurs for any reason, the following data will be collected prior to any other activities.

- Low Back Pain NRS (average low back pain in the last 24 hours)
- Report Adverse Events (if applicable)
- Complete and document device activities if applicable

Data will be collected according to the data collection schedule (Table 3).

Table 3: Data Collection Schedule

	1: Baseline Visit	2: Activation Visit about 14 Days Post- Surgery	3: 90±30 Days Post Activation	4: 180±30 Days Post Activation	5: 1 Year ±60 Days Post Activation	6: 2 Year ±60 Days Post Activation	Unscheduled Visit
Medical History including Pain Detect Questionnaire	✓						
Low Back Pain (NRS)	✓	✓	✓	✓	✓	✓	✓
ODI	✓		✓	✓	✓	✓	
EQ-5D	✓		✓	✓	✓	✓	
Percent Pain Relief (PPR)			✓	✓	✓	✓	
Subject Global Impression of Change (SGIC)			✓	✓	✓	✓	
Treatment Satisfaction Questionnaire (TSQ)			✓	✓	✓	✓	
Work Status Evaluation	✓		✓	✓	✓	✓	
Medications: Opioids	✓		✓	✓	✓	✓	
Health Care Utilization	✓				✓	✓	
Device Measurements & Stimulation Thresholds*		✓	✓	✓	✓	✓	✓
Adverse Events (AE's)		✓	✓	✓	✓	✓	✓

^{*}Device information will be collected at the implant procedure.

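### Subjects may enrol after implant, but adverse events are collected only from consent with no look-back, so the count of serious adverse device effects may be too low

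*Protocol*

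**What the plan says.** - **Scope.** Section 4.1 states the aim of identifying residual risks "by reporting all Serious Adverse Device Effects as well as performance and health care utilization through two years post-implant". The safety entry in the Registry Summary has the same window: "Assessment of all Serious Adverse Device Effects that occur through two years post-implant". Both run to two years from implant.
- **Entry.** Section 4.2 provides that "Subjects may decide to be enrolled in the registry before or after implant" and sets no maximum delay. It also states that "A minimum of 50 Subjects will be implanted at up to 25 sites".
- **Consent.** Section 4.9.1 requires consent before participation. Under section 4.7.1 the "Subject Informed Consent will be signed and recorded" at Visit 1.
- **Start of collection.** Section 4.7 notes that "once a Subject has consented to participate in the Registry Adverse Events will be collected at each visit". In Table 3 the adverse event row is ticked at Visits 2 to 6 and at unscheduled visits, but not at Baseline.
- **General wording.** Sections 4.4.1 and 4.4.3 ask for all adverse events without giving an onset date from which they count.

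**The concern.** The safety window opens at implant, but the collection rule opens at consent. The two coincide in practice for a Subject who consents before surgery. For a Subject who consents afterwards there is an interval that lies within the stated objective, and no procedure covers it. That interval includes the period just after surgery. Events there are in scope: the definition of an adverse device effect in Table 1 names implantation, and Table 2 has a procedure-related category.

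At stake is the registry's main claim, that it reports all SADEs from implant. The annual report to the Notified Body (section 4.4.4) covers SADEs reported in the Registry, so any gap carries through to it. An analysis plan cannot repair this, because it works only with the data that were collected.

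**Working it through.** **1. The passages side by side**

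| Question | Consent before implant | Consent after implant |
|---|---|---|
| Safety window opens (4.1, Registry Summary) | Implant | Implant |
| Collection opens (4.7, 4.7.1) | Before implant | At consent, after implant |
| First adverse event tick in Table 3 | Activation, the first tabulated visit after surgery | Activation; none at Baseline |
| Instruction to look back to implant | Not needed | None found |

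The blank Baseline cell suits the first column only. The nearest substitutes in Table 3 are medical history at Baseline and device information at the implant procedure. Neither is an adverse event record.

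**2. Length of the uncovered interval**

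If a late enrollee follows the visit order, Visit 1 precedes activation, which is planned about 14 days after surgery (sections 4.7 and 4.7.2). The interval is then at most about two weeks. That is not a ceiling. Section 4.2 sets no limit, and under section 4.7.2, if the Subject cannot use the device because of, for example, injury, infection or a new condition, "then the activation visit may be postponed to allow the issue to resolve".

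**3. The plan's own figure**

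Section 4.8 claims 80% power to observe at least one event at a rate of 3.2% with 50 Subjects:

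1 − (1 − 0.032)^50 = 1 − 0.968^50 = 80.3%.

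The stated figure is correct, provided every Subject is observed over the whole window.

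**4. What the gap could cost**

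Let f be the share of Subjects enrolled after implant and q the share of their SADE risk that falls before consent. The protocol gives neither, so both are assumptions.

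- Share of SADEs missed = f × q, whatever the number of Subjects.
- Probability of at least one recorded event with exactly 50 Subjects = 1 − 0.968^(50(1 − f)) × (1 − 0.032(1 − q))^(50f).

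| f | q | Missed, f × q | Probability of at least one |
|---|---|---|---|
| 0 | any | 0% | 80.3% |
| 10% | 10% | 1% | 80.0% |
| 10% | 50% | 5% | 78.7% |
| 10% | 100% | 10% | 76.9% |
| 20% | 10% | 2% | 79.7% |
| 20% | 50% | 10% | 76.8% |
| 20% | 100% | 20% | 72.8% |

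For example, with f = 20% and q = 50%: 1 − 0.968^40 × 0.984^10 = 76.8%. The rows with q = 100% apply only to an event type confined to the time before consent.

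**5. Enrolling more than the minimum**

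Fifty is a minimum. At f = 20%, 50 / 0.8 = 62.5, so 63 implanted Subjects with 13 enrolled late leave 50 observed from implant. The probability is again 1 − 0.968^50 = 80.3%, even at q = 100%. Extra Subjects restore the chance of seeing an event. They do not change the share of SADEs missed.

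**The case against.** The best reply is that section 4.7 fixes when a site collects adverse events, not which onset dates count. It may only restate that consent must come first. Since consent is signed at Visit 1, collection at each visit could include Visit 1, in which case the blank Baseline cell sits awkwardly with section 4.7 itself. Other text points towards capture from implant. The objective covers all SADEs; sections 4.4.1 and 4.4.3 set no onset limit; section 4.4.2 classifies events in the 30 days after implant surgery; and Table 3 has an adverse event tick at activation. Long delays also fit poorly with a design whose change scores are measured from Baseline. Finally, every figure for the loss rests on assumed values, and at q = 10% the change is immaterial.

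Much of this stands. A site could report earlier events unprompted, the interval may usually be short, and the loss may be nil. Lost events may also still be found in site records while these are available, although not by analysing the registry data. But these passages show what a site might do, not what it is told to do. A site following section 4.7 and Table 3 as written would not look back, and practice could differ among up to 25 sites. Section 4.4.2 limits how some events are categorised; it does not require events from before consent to be gathered.

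**Conclusion.** The concern holds. For Subjects enrolled after implant, the protocol promises all SADEs from implant but gives no instruction to collect those that occur before consent. Through this gap the error can only lower the count, which is the unfavourable direction for a safety registry.

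The size cannot be determined from the protocol. It is zero if nobody enrols late, if no SADE falls in the interval, or if sites report such events unprompted. Under the assumed values above, 1% to 20% of SADEs would be missed, and the upper end needs both 20% late enrolment and events confined to the time before consent. The sample size statement in section 4.8 is arithmetically right and is not in dispute. The absence of a look-back instruction is certain on the text; the undercount is possible, not shown. The point should be fixed because the gap touches the main objective and is cheap to close.

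**What to change.** Amend section 4.7 and Table 3 as follows:

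- For Subjects enrolled after implant, collect at Visit 1, from site records, all adverse events from the implant date to consent. Classify them for seriousness and relatedness in the same way as other events.
- Add an adverse event tick in the Baseline column of Table 3 for these Subjects.
- Record in the registry data the implant date, the consent date and whether enrolment came before or after implant, so that SADEs can be shown for each group. The dates should already exist at the site, so this adds little work.
- Check that the consent form covers data from before consent.

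The choice of denominator and time at risk can be left to the analysis plan. The look-back does not reach patients who were implanted but never enrolled, which is a further reason to show the two groups separately.

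The cost is a short amendment, a brief chart review for each late enrollee and a check of the consent wording. The reported SADE count may rise.
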